9.6. Pregnancy

Pregnancy is not regarded as an AE unless there is a suspicion that a IMP may have interfered with the effectiveness of a contraceptive medication. Any pregnancy that occurs during study participation or up to 28 days after the final dose of IMP must be reported to [REDACTED] by phone or email, within 2 weeks of learning of its occurrence. [REDACTED] will send the Exposure in Utero Form to the site for completion within 24 hours. This form should be completed and returned to [REDACTED] within 24 hours of receipt.

All SAEs occurring in association with a pregnancy, brought to the Investigator's attention after the participant has completed the study must be promptly reported to [REDACTED]

Please see [Appendix 14.3 Contraceptive Guidance and Collection of Pregnancy Information](#) for further information.

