5.1. Inclusion criteria

To be eligible to participate in this study, all of the following criteria must be met:

1. Must have given written informed consent (signed and dated) and any authorizations required by local law and be able to comply with all study requirements.
2. Males or females aged ≥ 18 and ≤ 75 years old at the time of informed consent.
3. A diagnosis of atopic dermatitis (AD) meeting Hanifin and Rajka criteria for AD at screening ([Appendix 14.1](#)) with patient- or clinician- reported disease duration of at least 6 months.
4. Have severity of atopic dermatitis meeting the below criteria at both Screening and Day 1:
 - i. An IGA of 2, 3 or 4 on the vIGA scale, and;
 - ii. A BSA of $\geq 5\%$, and;
 - iii. An EASI score of ≥ 6 .

A cap will be set for each of the three IGA severity grades. When this cap is reached, Sponsor will notify sites that participants with severity score at Screening and/or Day 1 matching the closed stratum should be considered ineligible according to Inclusion Criterion 4i.

5. All participants must agree to use a bland additive-free, sodium lauryl sulfate (SLS)-free, and fragrance-free emollient cream, gel or ointment twice daily (or more, as needed) for at least 14 consecutive days immediately prior to randomization and must continue this treatment twice daily throughout the trial. See [Section 6.9.1.1. Background Therapy](#).
6. Meet the following contraception criteria:
 - i. Male participants:
 - i. A male participant must agree to use contraception as detailed in [Appendix 14.3](#) of this protocol during their participation in this study and for a period of 90 days after the last dose and refrain from donating sperm during this period.
 - ii. Female participants:
 - i. A female participant is eligible to participate if she is not pregnant, not breastfeeding, and at least 1 of the following conditions applies:
 1. Not a WOCBP as defined in [Appendix 14.3](#) or
 2. A WOCBP who agrees to follow the contraceptive guidance in [Appendix 14.3](#) during their participation in this study, 28 days prior to the first dose and for at least 1 complete menstrual cycle (≥ 30 days) after the last dose.

Agrees to not increase their usual sun exposure significantly during the study.

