7.7. Week 16 Visit

This visit will take place 113 days (± 3 days) after the Day 1 Visit. Participants may dose at home on the day of the visit. Prior to the visit, the participant will be asked to withhold the application of the emollient, and where safe, sunscreen and any other topical products until after all study assessments have been performed. See [Section 6.9.1.1 Background Therapy](#).

The following procedures will be performed:

- Perform full physical examination
- Measure vital signs including weight
- Perform 12-lead ECG
- Collect blood for safety labs as well as serum immune protein markers and inflammatory markers
- Collect urine for urinalysis
- Perform urine pregnancy test for WOCBP
- Take digital photographs of the same body locations taken at the Day 1 Visit
- Perform AD rating scales, including vIGA, EASI (and BSA), and SCORAD
- Perform patient reported clinical rating scales – HADS, POEM, DLQI, ADCT and SF-12
- Review and document concomitant medications and therapies including emollient use
- Assess and document adverse events (AEs)
- Confirm patient took IMP per protocol and recorded this via the eDiary
- Collect all remaining empty and unused study wallets/cartons dispensed at the Week 2, Week 4 and Week 8 Visits

Open Label Extension Option

Participants who complete the 16 weeks of double-blind treatment may have the option to enter an Open Label Extension (OLE) protocol at the Week 16 Visit, if available. A separate consent form must be signed prior to the Week 16 Visit, however, only those participants that complete all 16 weeks on study IMP (active or placebo) will be allowed to participate in the OLE.

Participants who do not enroll into the OLE will enter a 4-week follow-up period and complete the Week 20 Visit per the SOA.

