14.3. Contraceptive Guidance and Collection of Pregnancy Information

Definitions

Woman of Child-Bearing Potential (WOCBP)

A woman is considered fertile following menarche and until becoming postmenopausal unless permanently sterile (see below).

Women in the following categories are not considered WOCBP:

1. Premenarchal
2. Premenopausal female with 1 of the following:
 - Documented hysterectomy
 - Documented bilateral salpingectomy
 - Documented bilateral oophorectomy
 - Documented bilateral tubal ligation

Note: Documentation can come from the site personnel's review of the participant's medical records, medical examination, or medical history interview.

3. Postmenopausal female
 - A postmenopausal state is defined as no menses for 12 months prior to the Screening Visit without an alternative medical cause. In the absence of 12 months of amenorrhea, postmenopausal women will be assumed to be WOCBP and will need to follow contraceptive guidance and have pregnancy tests performed throughout the course of the study per the Schedule of Activities (SOA).
 - Females on HRT and whose menopausal status is in doubt will be required to use one of the non-oestrogen hormonal highly effective contraception methods if they wish to continue their HRT during the study.

Contraception Guidance

Male participants with a female partner of child-bearing potential must either

- Be abstinent from penile-vaginal intercourse as their usual and preferred lifestyle (abstinent on a long term and persistent basis) and agree to remain abstinent
- Use a male condom during each episode of penile penetration during their participation in the study and for 90 days after the last dose of IMP.
- Have a confirmed vasectomy.

In addition, all male participants must refrain from donating sperm for the duration of the study and for at least 90 days following their last dose.

Female participants

Female participants of child-bearing potential are eligible to participate if they agree to use a highly effective method of contraception consistently and correctly as described in [Table 14-1](#) below.

Table 14-1: Highly Effective Contraceptive Methods

Highly Effective Contraceptive Methods That Are User Dependent^a Failure rate of < 1% per year when used consistently and correctly.

Combined (oestrogen and progestogen containing) hormonal contraception associated with inhibition of ovulation^b.
 
 • Oral • Intravaginal • Transdermal

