
Progestogen only hormonal contraception associated with inhibition of ovulation
 
 • Oral • Injectable

Highly Effective Methods That Are User Independent^a
 
 • Implantable progestogen only hormonal contraception associated with inhibition of ovulation^b. • Intrauterine device (IUD) • Intrauterine hormone-releasing system (IUS) • Bilateral tubal occlusion

Vasectomised partner A vasectomised partner is a highly effective contraception method provided that the partner is the sole male sexual partner of the WOCBP and the absence of sperm has been confirmed. If not, an additional highly effective method of contraception should be used.

Sexual abstinence Sexual abstinence is considered a highly effective method only if defined as refraining from heterosexual intercourse during the entire period of risk associated with the study intervention, including at least 1 complete menstrual cycle (cycle \geq 30 days) for women and 90 days for men post last dose. The reliability of sexual abstinence needs to be evaluated in relation to the duration of the study and the preferred and usual lifestyle of the participant.

NOTES:
 
a) Typical use failure rates may differ from those when used consistently and correctly. Use should be consistent with local regulations regarding the use of contraceptive methods for participants participating in clinical studies.
 
b) Hormonal contraception may be susceptible to interaction with the study intervention, which may reduce the efficacy of the contraceptive method. In this case, a highly effective method of contraception plus condoms should be utilised during their participation in the study up to and including at least 1 complete menstrual cycle (\geq 30 days) for women and 90 days for men post last dose.

Pregnancy Testing

- WOCBP should only be included after a confirmed menstrual period and a negative pregnancy test.
- Pregnancy testing is required at screening.
- Pregnancy testing will be performed whenever a menstrual cycle is missed or when pregnancy is otherwise suspected.

Collection of Pregnancy Information

Male participants with partners who become pregnant

- The Investigator will attempt to collect pregnancy information on any male participant's female partner who becomes pregnant while the male participant is in this study. This applies to all male participants who receive EDP1815.

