- After obtaining the necessary signed informed consent from the pregnant female partner directly, the Investigator will record pregnancy information on the appropriate form and submit it to the Sponsor within 24 hours of learning of the partner's pregnancy. The female partner will also be followed to determine the outcome of the pregnancy. Information on the status of the mother and child will be forwarded to the Sponsor. Generally, the follow-up will be no longer than 8 weeks following the estimated delivery date. Any termination of the pregnancy will be reported regardless of foetal status (presence or absence of anomalies) or indication for the procedure.

Female participants who become pregnant

- The investigator will collect pregnancy information on any female participant who becomes pregnant while participating in this study. Information will be recorded on the appropriate form and submitted to the Sponsor within 24 hours of learning of a participant's pregnancy. The participant will be followed to determine the outcome of the pregnancy. The investigator will collect follow-up information on the participant and the neonate and the information will be forwarded to the Sponsor. Generally, follow-up will not be required for longer than 6 to 8 weeks beyond the estimated delivery date. Any termination of pregnancy will be reported, regardless of foetal status (presence or absence of anomalies) or indication for the procedure.
- While pregnancy itself is not considered to be an AE or SAE, any pregnancy complication or elective termination of a pregnancy will be reported as an AE or SAE. A spontaneous abortion is always considered to be an SAE and will be reported as such. Any post-study pregnancy related- SAE considered reasonably related to the study intervention by the Investigator will be reported to the Sponsor as described in **Section 9.5 Reporting Serious Adverse Events**. While the Investigator is not obligated to actively seek this information in former study participants, he or she may learn of an SAE through spontaneous reporting.
- Any female participant who becomes pregnant while participating in the study will discontinue study intervention or be withdrawn from the study.

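### Men must use contraception for 90 days after the last dose, but the duty to report a partner's pregnancy ends at about 28 days, leaving nominally 62 days with no rule to report the pregnancy or follow its outcome

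*Protocol*

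**What the plan says.** **Contraception.** Protocol 5.1, criterion 6, has male participants use contraception during the study and "for a period of 90 days after the last dose and refrain from donating sperm during this period". Appendix 14.3 sets out what this means for a man with a female partner of child-bearing potential: long-term abstinence, a confirmed vasectomy, or a condom "during their participation in the study and for 90 days after the last dose of IMP". The abstinence entry in Table 14-1 describes refraining "during the entire period of risk associated with the study intervention" and gives the post-dose part of that period as at least one menstrual cycle "for women and 90 days for men post last dose".

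**Reporting.** Section 9.6 states: "Any pregnancy that occurs during study participation or up to 28 days after the final dose of IMP must be reported". It does not say whether partners are meant. Appendix 14.3 does address partners. The investigator tries to collect information on a partner "who becomes pregnant while the male participant is in this study", subject to her consent, and the rule is confined to men who receive EDP1815. Once a pregnancy has been collected, "The female partner will also be followed to determine the outcome of the pregnancy", generally for no more than 8 weeks after the estimated delivery date.

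**End of participation.** A man who completes treatment and does not enter the extension leaves at the Week 20 visit (7.8). After early termination the end-of-study date is a telephone call 28 days (+3) after the last dose (7.9).

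**The concern.** The protocol asks men to prevent pregnancy for 90 days, yet stops collecting partner pregnancies after roughly a third of that time. For women the two periods nearly agree: at least 30 days of contraception after the last dose against 28 days of reporting. For men they do not, and no reason is given.

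What would be lost is limited but real. A partner pregnancy that begins in the uncovered days and has no complication known to the site need not be recorded. Outcome follow-up under 14.3 starts only from a collected pregnancy, so nothing would prompt the site to learn how it ended.

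There is a second, practical difficulty. Treatment within a cohort is blinded (6.10), so a site cannot tell which men received EDP1815. It therefore cannot apply the 14.3 partner rule as worded.

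**Working it through.** This is day arithmetic.

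**Inputs**
- Male contraception after last dose: 90 days (5.1; 14.3).
- Reporting under 9.6: during participation or up to 28 days after the final dose, read here as whichever ends later.
- Reporting under 14.3: participation only.
- Week 16 visit: "This visit will take place 113 days" after Day 1, window 3 days either way, so 110 to 116 (7.7).
- Week 20 visit: 141 days, window +3, so 141 to 144 (7.8).
- Early-termination call: 28 to 31 days after last dose (7.9).

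**The plan's own figure.** Follow-up = 141 - 113 = 28 days, which reproduces the 4-week follow-up period in 4.2.

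**Nominal gap.** 90 - 28 = 62 days; 62/90 = 69%. Early and late windows move this a little.

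**With visits in window.** Week 20 minus Week 16 runs from 141 - 116 = 25 to 144 - 110 = 34 days.

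| Case | Days covered after last dose | Gap (90 minus covered) |
|---|---|---|
| Last dose on Week 16 visit day, 9.6 covers partners | 28 to 34 | 56 to 62 |
| Last dose the day before, 9.6 covers partners | 28 to 35 | 55 to 62 |
| Last dose on visit day, 14.3 alone governs partners | 25 to 34 | 56 to 65 |
| Last dose the day before, 14.3 alone | 26 to 35 | 55 to 64 |
| Early termination, call made | 28 to 31 | 59 to 62 |

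**These ranges are not bounds.**
- If dosing stopped on Day 103, 7 days before the earliest Week 16 visit, coverage could reach 144 - 103 = 41 days and the gap would be 49.
- Section 7.11.3.1 allows a Week 16 visit outside its window. As an illustration, a last dose on Day 125 with Week 20 on Day 141 to 144 leaves 16 to 19 days covered under 14.3 alone, a gap of 71 to 74.
- Participants are only asked to take the early-termination call. If it does not happen, the gap under 14.3 alone can exceed 62.
- Where 9.6 covers partners, its 28-day floor holds the gap at or below 62 in every case.

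**After the change below.** The rule would run to 90 days, so the gap in the rule is 90 - 90 = 0.

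**The case against.** The strongest reply is that this is a choice and not an error. A precautionary contraception period and a reporting period tied to safety follow-up serve different purposes, and nothing requires them to match. The 28 days agrees with the cutoff for new adverse events in 9.5.5. Section 3.2 states that EDP1815 has no systemic absorption, and no route is described by which a pregnancy some weeks after a man's last dose could be exposed. Serious outcomes are already caught: 9.6 requires prompt reporting of pregnancy-associated serious adverse events that come to the investigator after the participant has completed the study, and 9.3 counts a congenital anomaly as serious whether the participant is male or female.

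Most of this stands. A reader might infer a contradiction, but there is none, because a site can follow both windows. A reader might also infer that nothing about pregnancy is reportable after 28 days. That is wrong, since the serious-event rule in 9.6 carries no time limit. Nor do the documents establish the full 90 days as a risk period for men in general. The risk phrase appears in the abstinence entry of Table 14-1, and the operative male rules do not use it.

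What the reply does not remove is the dependence of outcome follow-up on a collected pregnancy. The serious-event rule works only if the event reaches the investigator, and without a recorded pregnancy the site has no reason to ask.

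**Conclusion.** The point holds as a minor gap in safety reporting. For men with a partner of child-bearing potential who do not enter the extension, nominally 62 of the 90 days have no rule to report the pregnancy itself or follow its outcome. This assumes dosing up to the Week 16 visit and visits on their target days. The figure shifts by a few days with visit windows and by more in the edge cases shown, so it is best quoted as nominal.

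The safety impact is small, because the protocol states there is no systemic exposure and contraception is still required on the days concerned. It would go too far to read this as evidence of fetal risk. The documents do not give the number of men, of men with such partners, or of extension entrants, so no count of missed pregnancies can be estimated. Sample size, power and the efficacy analyses are unaffected.

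**What to change.** Amend two places in the protocol.

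1. **Window.** In 9.6 and Appendix 14.3, require reporting of any partner pregnancy that occurs while the man is in the study or within 90 days of his last dose of IMP. In 14.3 this means adding the 90-day limb after "who becomes pregnant while the male participant is in this study". The duty should apply when the site learns of the pregnancy, with the partner's consent as 14.3 already requires.
2. **Who is covered.** In 14.3, make the partner rule apply to all men who receive IMP, in place of those who receive EDP1815. Section 6.1 includes placebo in IMP, so a blinded site can then apply the rule.

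The text should say that after the final visit or call, reporting depends on the participant making contact. No change is proposed for female participants.

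The cost is a short amendment, a notice to sites and an occasional post-study report. No visits or calls are added. The limitation is that reporting after the last contact is voluntary and will be incomplete.

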9.7. Overdose

Excessive dosing (greater than 4 capsules within 24 hours) should be recorded in the CRF. Participants will be instructed to contact the Investigator or study coordinator immediately in the event of a suspected overdose.

Any overdose must be promptly reported to [REDACTED] via the Special Situations Form. Overdose itself is not to be reported as an AE. However, any AEs or SAEs associated with the overdose are to be reported on relevant AE/SAE sections in the eCRF and on the Paper SAE Form provided to [REDACTED] ([Section 9.5 Reporting Serious Adverse Events](#)).

In the event of a symptomatic overdose, the Investigator should:

1. Manage the patient symptomatically with supportive care.
2. Contact the Medical Monitor urgently.
3. Document the quantity of the excess dose in the eCRF.
4. Document the overdose symptoms and their duration in the eCRF.

Doses of EDP1815 capsules that have previously been administered include a dose of 8.0×10^{11} cells taken once daily for 16 weeks, and 1.28×10^{12} cells taken once daily for 8 weeks. There are no specific expected adverse events expected in an overdose, but the participant should be closely and carefully monitored. There is no specific treatment or antidote, but supportive clinical care should be provided as dictated by the participant's clinical status.

Decisions regarding dose interruptions or modifications will be made by the Investigator in consultation with the Medical Monitor based on the clinical evaluation of the participant.

9.8. Safety Signal Detection

Selected data from this study will be reviewed periodically in a blinded fashion to detect as early as possible any safety concern(s) related to the IMP so that Investigators, clinical study participants, regulatory authorities, and IRBs/IECs will be informed appropriately and as early as possible.

The Study Physician or medically qualified designee/equivalent will conduct an ongoing review of SAEs. [REDACTED]DM will perform ongoing SAE reconciliations in collaboration with the PV representative.

As appropriate for the stage of development and accumulated experience with the IMP, medically qualified personnel at the Sponsor may identify additional safety measures (e.g., AEs, vital signs, laboratory or ECG results) for which data will be periodically reviewed during the course of the study.

9.9. Study Halting Criteria

The study will be halted if any of the following occur:

- One fatal SAE considered definitely, probably, or possibly related to the investigational product.

- Two or more participants with a non-fatal SAE considered definitely, probably, or possibly related to the investigational product.
- Three or more participants with grade 3 AEs of the same type considered definitely, probably, or possibly related to the investigational product.
- Any participant develops a documented *Prevotella histicola* infection in a sterile space confirmed by clinical culture and/or qPCR.

